#### **Visit 4 (Week 8)**

- Adverse event assessment
- Vitals (weight, blood pressure, temperature, heart rate)
- Subjects will return their unused study drug to the study team for IP accountability

#### **Concomitant Medications**

Subjects will be allowed and advised to continue with their current diarrhea treatments as long as it was at a stable dose for 30 days prior to randomization.

#### **Protected Health Information**

As the study is not industry-sponsored, no protected health information will be provided to any outside sources, excluding Prometheus Laboratories which is BIDMC's send out for BAM.

#### **Questionnaires/Efficacy Assessments**

Throughout the study subjects will be required to access their electronic diary every day via RedCap, preferably at the same time each day, to record bowel symptoms and rescue medication use.

- Bristol Stool Score (BSS)  
Patients will be asked to rate the BSS most representative of the past 24 hours. The patient-reported BSS consistency score is based on a 1 to 7 scale where 1 corresponds to a hard stool and 7 corresponds to watery diarrhea.
- Frequency, Urgency and Incontinence  
Patients will be asked to record the number of bowel movements, number of incontinence episodes and the number of urgency episodes over the past 24 hours.
- Diarrhea - Adequate Relief  
Once per week patients will be asked whether they have experienced adequate relief of their diarrheal symptoms. The IBS-adequate relief (IBS-AR) score is a dichotomous single item used to assess adequate relief of IBS symptoms.
- Diarrhea - Quality of Life  
Patients will be asked to assess the impact of their IBS-like symptoms on their quality of life using the IBS-Quality of Life instrument (Patrick et al, 1998). The IBS-QoL will be completed at the study center at all visits. The IBS-QoL will be completed at the beginning of the applicable study visits before all other evaluations, especially discussion of AEs or the patient's medical condition.
- Worst Abdominal Pain Score  
Patients will be asked to rate their worst abdominal pain in the past 24 hours. The patient-reported worst abdominal pain will be recorded on a 0 to 10 scale, where 0 corresponds to no pain and 10 corresponds to worst imaginable pain.
- Abdominal Discomfort Score  
Patients will be asked to rate their abdominal discomfort in the past 24 hours. The patient-reported abdominal discomfort will be recorded on a 0 to 10 scale, where 0 corresponds to no discomfort and 10 corresponds to worst imaginable discomfort.
- Abdominal Bloating Score

Patients will be asked to rate their abdominal bloating in the past 24 hours. The patient-reported abdominal bloating will be recorded on a 0 to 10 scale, where 0 corresponds to no bloating and 10 corresponds to worst imaginable bloating.

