### B1. PURPOSE OF PROTOCOL

The primary objectives of this study are:

- To evaluate the clinical response of patients with diarrhea to crofelemer relative to placebo.
- To evaluate the overall safety and tolerability of crofelemer in the treatment of diarrhea.

The secondary objective of this study is assess whether improvement in bowel function with crofelemer is more effective in subjects without evidence of bile acid malabsorption (i.e., elevated C4 level).

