#### Visit 2 (Day 0)

- Adverse event assessment
- Vitals (weight, blood pressure, temperature, heart rate)
- Subjects who meet all conditions for study entry will be randomized into the 4-week double-blind treatment phase. Subjects will be randomized (1:1) to receive crofelemer 125 mg BID or placebo BID for 4 weeks. Approximately 80 patients will be randomly assigned (in a 1:1 ratio) to 125mg crofelemer bid vs. placebo.
- Subjects will continue to complete daily diary assessments of their bowel symptoms and use of loperamide during the 4-week treatment period via RedCap.

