### **B. Statistical Considerations**

#### ***Sample Size Justification:***

This study aims to recruit 120 subjects until 80 subjects are enrolled. This sample size is based on a 85% power calculation assuming placebo response is 40%.

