#### ***Data Analysis:***

All continuous variables will be tested for normality using the Shapiro-Wilk test. Normally distributed continuous data will be presented as mean ( $\pm$  SD) and will be compared pre-and post- interventions using paired Student's t-test. Continuous data which are not normally distributed will be presented as median (range) and compared using Wilcoxon signed-rank test. Proportions will be expressed as percentages and compared using chi-square test or fisher exact test as appropriate.

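### No primary endpoint, responder definition, significance level or multiplicity rule is set for nine unranked efficacy measures, and the 40% placebo response in the power statement is tied to none of them

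*Combined protocol and SAP*

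**What the plan says.** The first primary objective in B1 is "To evaluate the clinical response of patients with diarrhea to crofelemer relative to placebo". No variable, threshold, time point or missing-data rule follows.

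Sample Size Justification states "This study aims to recruit 120 subjects until 80 subjects are enrolled" and continues "This sample size is based on a 85% power calculation assuming placebo response is 40" (per cent). It gives no endpoint, no crofelemer response rate, no significance level and no sidedness. The Visit 2 section sets the allocation: "Approximately 80 patients will be randomly assigned (in a 1:1 ratio) to 125mg crofelemer bid vs. placebo".

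Questionnaires/Efficacy Assessments lists nine measures on an equal footing: Bristol Stool Score (BSS), bowel movements, incontinence episodes, urgency episodes, adequate relief, IBS-QoL, worst abdominal pain, abdominal discomfort and bloating. Most are daily; the BSS entry, for example, reads "Patients will be asked to rate the BSS most representative of the past 24 hours". Adequate relief is the only one defined as dichotomous, and it is weekly: "Once per week patients will be asked whether they have experienced adequate relief of their diarrheal symptoms". Rescue medication use goes into the same diary and could be counted as a tenth.

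Data Analysis begins "All continuous variables will be tested for normality using the Shapiro-Wilk test". It then assigns paired pre/post tests (t or Wilcoxon signed-rank) to continuous data and chi-square or Fisher tests to proportions. It names no primary comparison, significance level or multiplicity rule.

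**The concern.** The objective and the power statement both speak of response, but no measure is designated as the one that decides it. Two things follow.

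First, the 85% power and the assumption "assuming placebo response is 40" (per cent) cannot be attached to any test the trial will perform. A reader cannot judge whether 40% is a plausible placebo rate, or how large a drug effect the trial was built to detect.

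Second, the choice of measure, week and summary stays open until the data are seen. Adequate relief alone yields four binary answers per patient over the four double-blind weeks, which a single chi-square test does not handle until they have been reduced to one result. A favourable finding on one of nine measures could be presented as success, and no result on any one of them would count as failure.

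**Working it through.** **Inputs from the protocol.** 80 patients randomised 1:1, so 40 per arm; 85% power; placebo response 40%; nine efficacy measures (ten with rescue use).

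**Inputs the protocol does not give, assumed here.** Two-sided 5% level; between-arm comparison of every measure; a common correlation ρ between the test statistics, varied from 0 to 0.9.

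**Step 1: the plan's own figure.** N = 80 cannot be reproduced, because the crofelemer rate, significance level and sidedness are missing. It can only be solved backwards. With n per arm and p̄ the mean of the two rates,

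power = Φ( [ (p₂ − p₁) − z·√(2p̄(1−p̄)/n) ] / √( (p₁(1−p₁) + p₂(1−p₂))/n ) ).

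- At n = 40, p₁ = 0.40 and z = 1.960, 85% power needs p₂ ≈ 0.726: (0.326 − 1.960 × 0.1109)/0.1048 = 1.037, and Φ(1.037) = 0.85. The implied difference is about 33 percentage points.
- With a one-sided 5% test the implied crofelemer rate is about 69%. With a continuity correction it is about 75%.
- For 40% against 60%: (0.200 − 1.960 × 0.1118)/0.1095 = −0.175, so power is 43%, and 85% power would need 111 per arm.

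The power statement therefore fits quite different designs, and the text does not say which was meant.

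**Step 2: false-positive risk if all nine are compared between arms.** Under independence, the chance of at least one significant difference in either direction is 1 − 0.95⁹ = 0.370. The chance of at least one favouring crofelemer is 1 − 0.975⁹ = 0.204. For equicorrelated normal test statistics with c = 1.960 and k = 9, the either-direction risk is

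1 − ∫ φ(x) [ Φ((c − √ρ·x)/√(1−ρ)) − Φ((−c − √ρ·x)/√(1−ρ)) ]ᵏ dx,

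and the risk favouring crofelemer drops the second Φ term.

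| ρ | Either direction | Favouring crofelemer |
|---|---|---|
| 0 | 37.0% | 20.4% |
| 0.3 | 32.6% | 16.5% |
| 0.5 | 26.9% | 13.5% |
| 0.7 | 20.2% | 10.1% |
| 0.8 | 16.6% | 8.3% |
| 0.9 | 12.4% | 6.2% |
| One test | 5% | 2.5% |

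With rescue use as a tenth measure, the either-direction figures are 40.1% at ρ = 0 and 21.3% at ρ = 0.7. Picking among weeks would add to the risk; that is not quantified here.

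**Step 3: Data Analysis read literally.** Eight of the nine measures are scores or counts. If they are treated as continuous, they get pre/post tests, which do not compare crofelemer with placebo. Only proportions could be compared between arms, and adequate relief is the only ready-made proportion. Its four weekly answers have no combining rule, so the choice of week and summary remains open on this reading too.

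**Step 4: price of keeping nine co-equal endpoints.** Bonferroni gives 0.05/9 = 0.0056 per test. For 40% against 72.6% at 40 per arm, power falls from 85% to about 57%, and about 66 per arm would be needed to restore 85%.

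**The case against.** The strongest reply is that the inflation figures do not describe the written plan. No significance level appears anywhere, and Data Analysis does not prescribe nine between-arm tests; continuous measures get paired pre/post tests. That stands. A reader might infer that each measure is tested the same way at 5%, so that any efficacy claim carries a 20–37% false-positive risk. The documents do not support this. The level and the between-arm testing are assumptions, and 20–37% counts differences in either direction, including those favouring placebo. For a false claim in crofelemer's favour the matching range is about 10–20%. The lower end depends on stopping at correlation 0.7, which has no source in the text. Pain, discomfort and bloating share a 0–10 scale and a 24-hour recall, so stronger correlation, and hence lower risk, cannot be excluded.

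A reader might also infer that adequate relief must be the endpoint behind the 40%, as the only dichotomous instrument. That does not follow. Any score can be turned into a responder variable, and inclusion criterion 4 already applies a BSS cut-off of 5 for entry. Adequate relief is also described as an IBS measure, whereas the inclusion criteria enrol functional diarrhea.

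Nor does the earlier IBS-D trial described in B2 prove the point. It had a primary endpoint, missed it, and still reported a later finding.

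None of this supplies a primary endpoint. The objective is stated relative to placebo, so some between-arm comparison has to be made, and the plan does not say which.

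**Conclusion.** The concern holds as a gap in the plan. No primary endpoint, responder definition, significance level or multiplicity rule is given, and the 85% power and 40% placebo response belong to no identified test. This is more than missing detail, because the plan as written allows success to be claimed on any measure or week.

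The size is conditional. If nine measures are compared between arms at two-sided 5%, and the test statistics are equally correlated at between 0 and 0.9, the chance of at least one false result favouring crofelemer is about 20% down to 6%, against 2.5% for one test. In either direction it is about 37% down to 12%, against 5%. These figures show what the open choice could cost; they are not error rates of a stated procedure.

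**What to change.** Before unblinding, name one between-arm primary endpoint for the double-blind phase, with its responder definition, missing-data rule, test and significance level. Restate the sample size for that endpoint, giving the crofelemer rate assumed alongside the 40% and the 85%.

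A workable default, offered as a proposal, is the proportion of randomised patients reporting adequate relief on at least 2 of the 4 weekly ratings, with a missing week counted as no relief, crofelemer against placebo by chi-square at two-sided 5%. It uses data already being collected. The investigators may prefer another responder definition, provided it is fixed in advance.

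Report the remaining measures as between-arm differences with 95% confidence intervals, labelled supportive.

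The cost is protocol and SAP wording, with no new data. The false-positive risk for the primary claim returns to the chosen level without the loss of power that a nine-way Bonferroni split would bring. The downside is that p-values on the other measures no longer support an efficacy claim.

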### B3. DESCRIPTION OF RESEARCH PROTOCOL

#### A. Study Design – Overview, Methods, Procedures

This is a randomized, double-blind, placebo-controlled, parallel group, study is designed to evaluate the efficacy and safety of orally administered crofelemer in patients with diarrhea. The study will consist of a 2-week screening phase, a 4-week double-blind treatment phase, followed by a 4 week open-label extension for both groups.

#### Visit 1

- Informed Consent
- Baseline demographics, medical and treatment history
- Baseline questionnaires via RedCap
- Vitals (height, weight, blood pressure, temperature, heart rate)
- Blood draw for bile acid malabsorption (BAM); mast cell activation, i.e C4, tryptase, histamine; and storing of blood for future studies. BAM is a send-out lab performed by Prometheus Labs. Mast cell activation will be done at a research laboratory at BIDMC.
- Subjects meeting the inclusion and exclusion criteria will enter a screening period of up to 2 weeks during which time subjects will complete daily diary assessment of their bowel symptoms including bowel frequency and use of loperamide via RedCap.
- At the conclusion of the screening period, subjects will be evaluated to determine if they met study entry criteria related to diary compliance, loperamide rescue medication use, and stool consistency (i.e., Bristol Stool Score).

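### IBS-QoL: two pre-dose scores are expected, but the plan defines no baseline and has no between-arm model that would use them

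*Combined protocol and SAP*

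**What the plan says.** The quality-of-life item under Questionnaires/Efficacy Assessments (B3.A) states: "The IBS-QoL will be completed at the study center at all visits". It adds: "The IBS-QoL will be completed at the beginning of the applicable study visits before all other evaluations". Four visits are listed. After Visit 1, eligible subjects "will enter a screening period of up to 2 weeks". Visit 2 is Day 0: "Subjects who meet all conditions for study entry will be randomized into the 4-week double-blind treatment phase". An IBS-QoL taken at the start of Visit 2 therefore comes before randomisation and before any study drug.

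The schedule for Visit 1 has the entry "Baseline questionnaires via RedCap" without naming the instruments. The lists for Visits 2, 3 and 4 do not mention the IBS-QoL.

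Data Analysis (B3.B) has one rule for all continuous variables. If normally distributed, they "will be compared pre-and post- interventions using paired Student's t-test"; otherwise the Wilcoxon signed-rank test is used. It does not say which visit is pre, whether two pre values are combined, or how continuous outcomes are compared between arms.

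**The concern.** Two things are left open. First, there are two candidate baselines up to two weeks apart and no rule for choosing between them, so the choice could be made after the data are seen. If Visit 1 were used, any change during screening would be counted in the within-arm pre/post change, and a paired test has no control arm to subtract it.

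Second, the first objective in B1 is response relative to placebo, yet the only test offered for a continuous outcome is within-subject. A pre-dose score is most useful as a covariate in a between-arm model. The plan has no such model, so neither pre-dose score reduces the variance of the crofelemer–placebo difference. With about 40 patients per arm, that precision would be useful.

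**Working it through.** **Plan's own figure.** None exists for the IBS-QoL: no SD, correlation or target difference. The 80-subject calculation concerns a response proportion (85% power, 40% placebo response) and is not affected here.

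**Inputs.** From the documents: N = 80, allocated 1:1, with scores at Visit 1, Visit 2 (Day 0) and Visit 3 (Week 4). Assumed: equal variances (set to 1), a linear relation between scores, complete data, and the correlations r12 (Visit 1–Day 0), r13 (Visit 1–Week 4) and r23 (Day 0–Week 4).

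**Formulas.** Residual variance of the Week 4 score:
- adjusting for Visit 1 only: 1 − r13²
- adjusting for Day 0 only: 1 − r23²
- adjusting for both: 1 − (r13² + r23² − 2·r12·r13·r23)/(1 − r12²)

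Equivalent gain in patients = ratio of residual variances − 1.

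**Example (0.8, 0.6, 0.7).** Both: 1 − (0.36 + 0.49 − 0.672)/0.36 = 1 − 0.4944 = 0.5056. Over Visit 1: 0.64/0.5056 = 1.266. Over Day 0: 0.51/0.5056 = 1.009.

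| r12 | r13 | r23 | Visit 1 only | Day 0 only | Both | Gain over Visit 1 | Gain over Day 0 |
|---|---|---|---|---|---|---|---|
| 0.5 | 0.5 | 0.5 | 0.750 | 0.750 | 0.667 | 12.5% | 12.5% |
| 0.6 | 0.6 | 0.6 | 0.640 | 0.640 | 0.550 | 16.4% | 16.4% |
| 0.7 | 0.7 | 0.7 | 0.510 | 0.510 | 0.424 | 20.4% | 20.4% |
| 0.8 | 0.6 | 0.6 | 0.640 | 0.640 | 0.600 | 6.7% | 6.7% |
| 0.7 | 0.5 | 0.6 | 0.750 | 0.640 | 0.627 | 19.5% | 2.0% |
| 0.85 | 0.5 | 0.6 | 0.750 | 0.640 | 0.640 | 17.3% | 0.06% |
| 0.8 | 0.6 | 0.7 | 0.640 | 0.510 | 0.506 | 26.6% | 0.9% |
| 0.85 | 0.6 | 0.7 | 0.640 | 0.510 | 0.510 | 25.5% | 0.02% |

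These span 7–27% over Visit 1 and 0–20% over Day 0. They illustrate and do not bound: (0.8, 0.5, 0.7) gives 0.75/0.50, or 50%, over Visit 1, and (0.85, 0.5, 0.5) gives 0.750/0.730, or 2.8%, over either.

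**Cost of the second covariate.** With k roughly normal covariates, the expected variance of the arm difference is multiplied by (N − 3)/(N − 3 − k). At N = 80, going from one covariate to two multiplies it by 76/75 = 1.013. Net of that, the 20.4% gain becomes 1.204 × 75/76 = 1.188 (18.8%). The 0.9% gain becomes 1.0088 × 75/76 = 0.996, a loss of about 0.4%. The 0.02% gain becomes a loss of about 1.3%.

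**Where most of the gain lies.** Take all correlations at 0.5, 40 per arm, two-sided 0.05 and 85% power, without the 1.3% cost. The detectable difference is (1.960 + 1.036) × √(2v/40) SD, where v is the variance used:
- between-arm comparison of change scores from one pre value, v = 2 − 2(0.5) = 1.0: 0.67 SD
- ANCOVA on one score, v = 0.75: 0.58 SD
- ANCOVA on both, v = 0.667: 0.55 SD

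**Two covariates, not an average.** For (0.8, 0.6, 0.7), adjusting for the mean of the two scores leaves 1 − 0.65²/0.9 = 0.531, against 0.510 for Day 0 alone, which is 4% worse. Entering the scores separately avoids that loss, apart from the degree of freedom.

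**The case against.** The strongest objection is that Day 0 is at least as natural a baseline as Visit 1, and that against Day 0 the second score may add almost nothing. The 12–20% figures need Visit 1 to predict Week 4 as well as Day 0 does, although it is up to two weeks further away. If correlation decays with time, the gain shrinks to 2% or less in the table's unequal patterns, and the extra covariate can outweigh it. This stands, and the gain should not be called free.

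It also stands that two pre-dose scores are likely rather than certain. The text moves from all visits to the applicable ones, and the Visit 2 list names no questionnaire. Nothing exempts Visit 2, however.

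Three stronger readings are tempting, but the documents do not support them:
- **That the plan takes Visit 1 as the single baseline.** The Visit 1 entry names no instrument, and Data Analysis names no visit. What can be said is that baseline is undefined.
- **That change during screening biases the treatment comparison.** It would enter a within-arm change from Visit 1, but between randomised arms it cancels in expectation.
- **That both scores are unselected because the IBS-QoL is not an entry criterion.** Entry requires a stool-consistency threshold in the week before randomisation, which may select indirectly on quality of life. That does not bias the between-arm comparison either.

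Finally, it is fair to say that the missing between-arm analysis is the larger gap. That changes the emphasis but not the remedy, which supplies one for this outcome.

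**Conclusion.** The point holds as a cheap improvement. The documents imply two pre-dose IBS-QoL scores, leave the baseline undefined, and use neither score in a crofelemer–placebo comparison. The main benefit is a baseline-adjusted between-arm analysis at Week 4. Adding the second score is a conditional refinement: about 7–27% more patients compared with Visit 1 alone and 0–20% compared with Day 0 alone, less about 1.3% for the extra covariate. Against Day 0 the net result may be nil or slightly negative. All these figures rest on assumed correlations, equal variances and complete data on 80 patients. The effect is confined to the IBS-QoL, which is not named as primary, and does not bear on the sample size.

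**What to change.** In Data Analysis (B3.B), before unblinding, state that Week 4 (Visit 3) IBS-QoL is compared between crofelemer and placebo with a linear model (ANCOVA), with treatment arm, the Day 0 score and the Visit 1 score as terms, the two scores entered as separate covariates. Define Day 0 as the baseline for describing change. With the Day 0 score in the model, the estimated arm difference is the same whether the response is the Week 4 score or the change from Day 0.

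List the IBS-QoL under each visit in B3.A so that both pre-dose scores are sure to be collected, and say how a missing pre-dose score is handled.

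The cost is a few sentences and one degree of freedom. If all visits is meant as written, no new data or visits are needed.

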#### Rescue Medication for Uncontrolled Diarrhea

Subjects will be allowed to take loperamide rescue medication for the acute treatment of uncontrolled diarrhea. Loperamide at a unit dose of 2 -4 mg may be taken once approximately every 6 hours with the following guidelines:

- No more than 4 unit doses over a continuous 24-hour time period (8 mg/day)
- No more than 7 unit doses over a continuous 48 hour time period (14 mg over 2 days)
- No more than 11 unit doses over a continuous 7-day time period

Loperamide will not be provided to the subjects by the study team as it is standard of care for functional diarrhea.

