### **C. Subject Selection**

#### Inclusion Criteria

1. Patient is a man or woman aged 18 to 65 years, inclusive, at Screening.
2. Patient has functional diarrhea defined by the Rome IV criteria as loose (mushy) or watery stools  $\geq 25\%$  and hard or lumpy stools  $< 25\%$  of bowel movements
3. Patient has had a colonoscopy performed:
  - a. Within 10 years prior to Prescreening if patient is at least 50 years of age (alternatively, a flexible sigmoidoscopy, double contrast barium enema, or CT colonography within the past 5

- years is acceptable [see recommendations of the American Cancer Society])
- b. Since the onset (if applicable) of any of the following alarm features for patients of any age (see Spiller and Thompson, 2010 – i.e. Patient has documented weight loss within the past 6 months; Patient has nocturnal symptoms; Patient has a familial history of colon cancer; or patient has blood mixed with their stool (excluding any blood from hemorrhoids).
  4. Patient has an average daily stool consistency score (BSS) of  $\geq 5.0$  on days without the use of an anti-diarrheal and at least 3 days with a BSS score  $\geq 5$  on a 1 to 7 scale over the week prior to randomization.
  5. Patient has completed the daily diary on at least 6 of the 7 days during the week prior to randomization AND at least 11 of the 14 days during the 2 weeks prior to randomization.
  6. Patient has not used loperamide rescue medication more than 4 days during the screening period.
  7. Patient is not planning to change his/her usual diet and lifestyle during the course of the study.
  8. Patient is willing to be compliant with study procedures including completing the daily diary during the screening period and throughout the study.
  9. Patient must sign an informed consent document before the initiation of any study-related procedures indicating that he or she understands the purpose of and procedures required for the study and is willing to participate in the study.

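### Rescue loperamide: the milligram limits match the dose-count limits only at 2 mg per dose, yet up to 4 mg is allowed, and the plan does not say which limit governs

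*Combined protocol and SAP*

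**What the plan says.** The section Rescue Medication for Uncontrolled Diarrhea (B3, part A) lets subjects treat uncontrolled diarrhea with loperamide. On dose and interval it says: "Loperamide at a unit dose of 2 -4 mg may be taken once approximately every 6 hours". Three limits follow:

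- 24 hours: "No more than 4 unit doses over a continuous 24-hour time period (8 mg/day", closing the parenthesis there.
- 48 hours: "No more than 7 unit doses over a continuous 48 hour time period (14 mg over 2 days", likewise.
- 7 days: "No more than 11 unit doses over a continuous 7-day time period", with no milligram figure.

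The drug is not study supply: "Loperamide will not be provided to the subjects by the study team". Its use is self-reported. Visit 1 calls for a "daily diary assessment of their bowel symptoms including bowel frequency and use of loperamide via RedCap", and Visits 2 and 3 continue that diary through both treatment periods.

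The only other limit on loperamide is inclusion criterion 6: "Patient has not used loperamide rescue medication more than 4 days during the screening period". It counts days of use, not amount.

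**The concern.** The 24-hour and 48-hour lines each state a number of unit doses and a number of milligrams as if they were the same limit. They are the same only if every dose is 2 mg, and the preceding sentence allows up to 4 mg. For a subject taking more than 2 mg at a time, one half of the line can permit a dose that the other half forbids.

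Subjects buy and take the loperamide themselves, so the study does not control tablet strength or quantity through supply. This section holds the only limits on amount in the document. Staff who see three 4 mg doses in one day's record could not tell from the protocol whether the limit had been exceeded, and two people could classify the same day differently.

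The stakes are limited to how much rescue drug a subject may take over one or two days.

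**Working it through.** **Inputs**, all from Rescue Medication for Uncontrolled Diarrhea: unit dose 2 to 4 mg; interval about 6 hours; 4 doses or 8 mg per 24 hours; 7 doses or 14 mg per 48 hours; 11 doses per 7 days.

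**1. Reproduce the printed figures.** Implied unit dose = stated milligrams / stated count.

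- 24 hours: 8 / 4 = 2 mg
- 48 hours: 14 / 7 = 2 mg

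Both figures are exact at 2 mg per dose.

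**2. Apply the counts across the permitted range.** Amount = number of doses × mg per dose.

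| Window | At 2 mg | At 3 mg | At 4 mg | Printed |
|---|---|---|---|---|
| 24 h (4 doses) | 8 mg | 12 mg | 16 mg | 8 mg |
| 48 h (7 doses) | 14 mg | 21 mg | 28 mg | 14 mg |
| 7 days (11 doses) | 22 mg | 33 mg | 44 mg | none |

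If the counts govern, the 24-hour and 48-hour amounts are 1.5 times the printed figures at 3 mg and 2 times at 4 mg.

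**3. Apply the milligrams instead.** With every dose at 4 mg, 8 / 4 = 2 doses per 24 hours, and 14 / 4 = 3.5, so 3 whole doses per 48 hours. The printed counts of 4 and 7 cannot be reached at that dose. With a single 4 mg dose and the rest 2 mg, the most is 3 doses in 24 hours (4 + 2 + 2 = 8) and 6 in 48 hours (4 + 5 × 2 = 14).

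**4. Find where the readings part.** Running total at 4 mg every 6 hours:

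| Hour | Dose number | Total |
|---|---|---|
| 0 | 1 | 4 mg |
| 6 | 2 | 8 mg |
| 12 | 3 | 12 mg |
| 18 | 4 | 16 mg |

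The 8 mg figure is passed at dose 3 and the 14 mg figure at dose 4. Both doses are within the 4-dose count and the stated interval.

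**5. Check the weekly limit.**

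- If the counts govern, the 7-day maximum is 11 × 4 = 44 mg.
- If the milligrams bind, 44 mg is still reachable, for example with 4 mg at hours 0, 6, 31, 49, 56, 80, 98, 105, 129, 147 and 154. Neighbouring doses are at least 6 hours apart. Any three consecutive doses span at least 25 hours, so no 24-hour window holds more than 2 doses (8 mg). Any four span at least 49 hours, so no 48-hour window holds more than 3 doses (12 mg, under 14 mg).

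The choice of reading therefore does not change the weekly maximum.

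**6. Bound the number of high days.** If the counts govern and each dose is 4 mg, a day above 8 mg needs at least 3 doses. Three such days use 3 × 3 = 9 of the 11 weekly doses; four would need 4 × 3 = 12. At most 3 days in 7 can exceed 8 mg.

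**The case against.** The best reply is that each line is a single upper limit carrying both a count and an amount, so both apply and the stricter binds. A subject on 4 mg then stops at two doses in 24 hours, and 16 mg was never allowed. Letting the counts govern means ignoring two printed milligram figures. This reading is reasonable, and 16 and 28 mg should not be presented as what the plan evidently permits. But the text does not state it. A milligram figure in parentheses after a count reads at least as easily as a conversion, and under the stricter reading the printed counts are out of reach at a dose the same section allows.

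It can also be said that the consequences are small. The limits are introduced as guidelines, the drug is described as standard of care, no analysis depends on them, and the document gives no threshold that makes 12 or 16 mg a problem. All of that stands, and it keeps the point from being a major one. It does not remove the need for a self-administered dosing limit to have one meaning.

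Finally, any instructions given to subjects are not in the document, so confusion in practice is not shown. That also stands.

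**Conclusion.** The concern holds. The 24-hour and 48-hour limits agree with their own milligram figures only at 2 mg per dose. At the permitted 4 mg the two halves of each line differ by a factor of two (16 against 8 mg; 28 against 14 mg), and nothing elsewhere in the document reconciles them. For subjects who take only 2 mg at a time there is no discrepancy.

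Neither limit is shown to be wrong in itself; what is missing is which one applies above 2 mg. The conclusion rests only on the printed range, counts and milligrams, with no outside safety figure. Inclusion criterion 6 counts days, and neither Sample Size Justification nor Data Analysis uses loperamide amounts, so eligibility, power and the stated analyses are unaffected. The point should be fixed, but it is not critical.

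**What to change.** Keep the 2 to 4 mg range and state that the milligram limits bind. For example:

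> Each loperamide dose may be 2 to 4 mg, about 6 hours apart. The total must not exceed 8 mg in any 24 hours or 14 mg in any 48 hours, whatever the number of doses. No more than 11 doses may be taken in any 7 days.

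Because no dose is below 2 mg, these totals already imply the printed counts (8 / 2 = 4 and 14 / 2 = 7), so the counts can be dropped from the first two limits. The 7-day maximum stays at 44 mg.

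The alternative is to define the unit dose as 2 mg, which makes the printed 8 mg and 14 mg correct as they stand. It also removes the option of 4 mg at once and lowers the 7-day maximum from 44 mg to 11 × 2 = 22 mg. That is a clinical change which resolving the ambiguity does not require, so the first option is preferable.

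Either way the cost is a one-line amendment and the same wording in any subject instructions. Recording milligrams per day in the diary would help staff check the limit, but it is optional.
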